7 INVESTIGATIONAL PLAN

7.1 Description of Overall Study Design and Plan

This is a randomized, double-blind, placebo-controlled, multi-center, parallel-group study in adult and adolescent subjects (≥ 12 to 54 years) with moderate-to-severe AD. Eligible subjects must have a documented history of inadequate response to topical AD medication(s).

Approximately 245 subjects will be randomized 1:1 to receive either 30 mg nemolizumab (with a 60 mg loading dose) or placebo, stratified by baseline disease severity **CCI** **16.9**.

The study consists of 3 periods with up to 28 weeks total study duration: a 2- to 4-week screening period, a 16-week treatment period, and an 8-week follow-up period (12 weeks after the last study drug injection).

Screening Period

The screening period will evaluate subject eligibility. Subjects will apply a moisturizer at least once daily, beginning at screening. Subjects using a stable regimen of low- or medium-potency TCS with or without topical calcineurin inhibitor (TCI) at the screening visit (ie, ≥ 14 days prior to the baseline visit) should continue their therapy regimen. Subjects not using a stable regimen of TCS with or without TCI at the screening visit should not use these topical therapies during the study unless required as rescue therapy.

Rescue therapies are not permitted during the screening period.

Treatment Period

At the baseline visit, subjects will receive a loading dose of nemolizumab (60 mg) or placebo via 2 subcutaneous injections. Nemolizumab (30 mg) or placebo will then be administered via a single subcutaneous injection Q4W at Week 4, 8, and 12. At the Week 12 visit, subjects will also receive single doses of **PPD** **vaccines**. Clinical assessments will occur according to the schedule of assessments in **Table 4**.

This document is confidential.

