Subjects will continue to apply a moisturizer at least once daily. Subjects using background topical therapy (TCS with or without TCI) from the screening visit will continue use in the treatment period, which should be adjusted according to the disease activity and tolerability, based on investigator clinical judgment. (Subjects not using background topical therapy from the screening visit should not apply background topical therapy in the study.) If deemed to be medically necessary by the investigator (eg, to control intolerable AD signs/symptoms), topical and/or phototherapy rescue therapies can be prescribed to any subject at any time during the study, except during the screening period.

Subjects who complete the Week 16 treatment period may be eligible to enroll into an LTE study (Protocol 118163).

Follow-Up Period

The follow-up visit is not required for subjects who participate in the LTE study.

Subjects who decline or are not eligible to enter into the LTE study will complete a follow-up visit at Week 24 (12 weeks after their last study drug injection).

[figure not shown]
Subjects who discontinue the study prematurely should complete an early termination visit and a follow-up visit 12 weeks after their last study drug injection.

The follow-up visit will be conducted 8 weeks after completing the treatment period and/or 12 weeks after the last study drug injection. Twelve weeks corresponds to approximately 5 half-lives when nemolizumab 30 mg is dosed subcutaneously every 4 weeks.

An IDMC will review and monitor subject safety throughout the study, and an IAC will review all asthma-related AEs. Details on the IDMC and IAC, including the plan of analysis for outputs, the composition of the committees, the procedures, roles, responsibilities and their communications are provided in the IDMC and IAC charters, respectively.

An overview of the study design is present in [Figure 1](#).

Figure 1: Study Design

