## 6.6. Subgroups

Subgroup analysis will be performed in an exploratory manner to investigate the treatment effect across various subgroup. The following subgroup analyses will be performed for the primary and secondary vaccine response endpoints:

- By age (<18 years; >=18 years)
- By sex (Male, Female)
- By race (White, Black or African American, Asian, Other)
- CCI
- Baseline Weight (≤Q1, <Q1 median, <median Q3, > Q3)
- Baseline Weight (≤90 kg, > 90 kg)
- Coronavirus disease-19 (COVID-19) Infection (Subjects infected by COVID-19, Subjects not infected)
- Background therapy (subjects with background therapy, subject without background therapy)

In addition, analyses will be performed on the last subgroup (background therapy) for selected secondary efficacy endpoints.

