#### 7.6. Medications/Therapies

Prior medications/therapies are defined as medications/therapies which stop before 1st injection of study drug. Concomitant medications/therapies are defined as medications/therapies which start or stop on or after the 1st injection of study drug.

If start and/or stop dates of medications and therapies are missing or partial, the dates will be compared as far as possible with the date of first dose of study drug. Medications and therapies will be assumed to be Concomitant, unless there is clear evidence (through comparison of partial dates) to suggest that they started and stopped prior to the first dose of study treatment. If there is clear evidence to suggest that the medication or medical and surgical procedure started and stopped prior to the first dose of study drug, they will be assumed to be Prior.

For prior and concomitant medications, incomplete (i.e., partial missing) start dates and/or stop dates will be imputed using the algorithm described in Section 6.3.

Medications will be coded using the World Health Organization's Drug Dictionary (WHO DD) Version Global B3 SEP 2019 using the Preferred Anatomical Therapeutic Chemical (ATC) terms. TCI and TCS will be automatically identified using the following rule:

- TCS will be identified by ATC code "D07A".
- TCI will be identified by ATC code "D11AH" and with standardized medication name "TACROLIMUS" and "PIMECROLIMUS".

Prior and Concomitant medications will be summarized separately by Anatomical Therapeutic Chemical (ATC) level 2, level 4, and preferred name in frequency tables using ITT, mITT and safety population. Subjects with more than one medication in a given ATC level and preferred name will be counted only once in that category. It will be sorted in descending frequency of ATC level and of PT within ATC level term.

The following summaries will be produced:

- Prior medication
- Concomitant medication
- Rescue medication during treatment period (ITT Population only)
- Rescue medication during follow-up period (ITT Population only)

Sponsor: Galderma S.A./Galderma R&D, LLC; Protocol No.: RD.06.SPR.118380 V4.0, 06Jul2022

 Background therapy (ITT Population only) consisting of TCS and TCI with start date prior to study drug administration and that are not classified as rescue therapy

All medications will be listed. The background TCS dispensation/receipt will also be listed.

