# 14. Changes from Analysis Planned in Protocol

### 14.1. Concomitant Medications and Therapies

In protocol Section 9.6 (Prior and Concomitant Therapies), concomitant medications/therapies are defined as any therapies taken during the study (ie, from the screening visit to the end of study).

However, for the analysis purpose, the medications are classified as taken prior or concomitantly with the study drug administration. Concomitant medications/therapies are defined as medications/ therapies which start or stop on or after the 1st injection of study drug. The purpose of this analysis is to provide information separately on:

- the medication taken in addition to the study drug;
- the medication taken prior to the study drug administration.

This analysis could be used to identify any medication that could potentially interact with the study drug.

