# 17. Index of Tables

Table Number	Name	Analysis Set
14.1.1.1	Subject Disposition	Screened
14.1.1.2	Subject Accounting by Overall and Site	Population Screened
14.1.1.3	Subject Accounting by Visit	Population ITT
14.1.2	Major and COVID19-related Protocol Deviations	ITT
14.1.3.1.1	Demographic and Baseline Characteristics	ITT
14.1.3.1.2	Demographic and Baseline Characteristics	SAF
14.1.3.1.3	Demographic and Baseline Characteristics	mITT
14.1.3.2.1	Summary of Medical History	ITT
14.1.3.2.2	Summary of Medical History	Safety
14.1.3.2.3	Summary of Medical History	mITT
14.1.3.3.1	Summary of Prior Medical and Surgical Procedure	ITT
14.1.3.3.2	Summary of Concomitant Medical and Surgical Procedure	ITT
14.1.4.1.1	Summary of Prior Medications	ITT
14.1.4.1.2	Summary of Prior Medications	Safety
14.1.4.1.3	Summary of Prior Medications	mITT
14.1.4.2.1	Summary of Concomitant Medications	ITT
14.1.4.2.2	Summary of Concomitant Medications	Safety
14.1.4.2.3	Summary of Concomitant Medications	mITT
14.1.4.3.1	Summary of Rescue Medications during Treatment Period	ITT
14.1.4.3.2	Summary of Rescue Medications during Follow-up Period	ITT
14.1.4.3.3	Summary of Background Therapy	ITT
14.1.5.1.1	Summary of Vaccine and Study Drug Exposure and Compliance	SAF
14.2.1.1.1	Primary Analysis of Proportion of Subjects with a Positive IgG Response to Tetanus Toxoid at Week 16	mITT
14.2.1.1.2	Sensitivity Analysis of Proportion of Subjects with a Positive IgG Response to Tetanus Toxoid at Week 16 – Missing as Non-Responder	ITT
14.2.1.1.3	Sensitivity Analysis of Proportion of Subjects with a Positive IgG Response to Tetanus Toxoid at Week 16 – Observed Case	ITT
14.2.1.1.4	Sensitivity Analysis of Proportion of Subjects with a Positive IgG Response to Tetanus Toxoid at Week 16 – COVID-19 Affected Case	ITT
14.2.2.1.1	Analysis of Proportion of Subjects with a Positive IgG Response to Tetanus Toxoid at Week 16 using Different Criteria	mITT
14.2.2.1.2	Sensitivity Analysis of Proportion of Subjects with a Positive IgG Response to Tetanus Toxoid at Week 16 using Different Criteria – Missing as Non-Responder	ITT
14.2.2.1.3	Sensitivity Analysis of Proportion of Subjects with a Positive IgG Response to Tetanus Toxoid at Week 16 using Different Criteria – Observed Case	ITT
14.2.2.1.4	Sensitivity Analysis of Proportion of Subjects with a Positive IgG Response to Tetanus Toxoid at Week 16 using Different Criteria – COVID-19 Affected Case	ITT

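### SAP 7.6 identifies background therapy by start date alone, so read literally it counts topicals already stopped by screening

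*SAP*

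**What the plan says.** SAP 7.6 first separates prior from concomitant medication by stop date: "Prior medications/therapies are defined as medications/therapies which stop before 1st injection of study drug". It identifies TCS and TCI automatically, TCS by ATC code and TCI by ATC code plus drug name, and states no potency condition. It then lists a background therapy summary on the ITT population, "consisting of TCS and TCI with start date prior to study drug administration and that are not classified as rescue therapy". SAP Section 17 carries this as Table 14.1.4.3.3, "Summary of Background Therapy".

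SAP 6.6 makes presence or absence of background therapy an exploratory subgroup for the primary and secondary vaccine response endpoints, and adds that "analyses will be performed on the last subgroup (background therapy) for selected secondary efficacy endpoints". It does not define the term or refer to a definition.

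Protocol 7.1 ties background therapy to the screening visit. On those with a regimen: "Subjects using background topical therapy (TCS with or without TCI) from the screening visit will continue use in the treatment period". On those without: "Subjects not using a stable regimen of TCS with or without TCI at the screening visit should not use these topical therapies", except as rescue. Protocol 9.6.1.1 gives the same rule and limits TCS to low or medium potency. SAP 3.3 repeats the design text of Protocol 7.1.

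**The concern.** The 7.6 rule is a filter that a programmer can apply directly, and it is wider than the protocol's meaning. A corticosteroid cream that ended before screening started before study drug and is not rescue, so it passes. Under the same section it is also a prior medication, and nothing in 7.6 makes the prior and background categories mutually exclusive.

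What is at stake is the descriptive picture of how many subjects were on background topicals during the trial and, conditionally, the make-up of an exploratory subgroup. If the subgroup uses this flag, part of the group labelled as having background therapy would be off topicals, and a comparison between the two subgroups would no longer describe the distinction that the protocol draws.

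**Working it through.** There is no figure in the plan to reproduce and no formula applies. The check is to run typical medication records through both definitions.

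**Conditions in each definition**
- SAP 7.6: (i) TCS or TCI; (ii) started before study drug; (iii) not rescue.
- Protocol 7.1 and 9.6.1.1, with SAP 3.3: (i) TCS of low or medium potency, with or without TCI; (ii) stable regimen; (iii) in use at the screening visit.

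**Records compared**

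| Record | SAP 7.6 as written | Protocol |
|---|---|---|
| Stable medium-potency TCS at screening, continued | Background | Background |
| Same regimen at screening, stopped between screening and Day 1 | Background | Can be background |
| TCS or TCI stopped before screening | Background | Not background |
| Non-stable TCS or TCI stopped before Day 1 | Background | Not background |
| Topical first started after Day 1 as rescue | Not background | Not background |

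The definitions part on the third and fourth rows. The second row is not a conflict, so the remedy should not demand use on Day 1.

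**Does the rescue condition remove those two rows?** No. Under Protocol 9.6.1.3, rescue during screening makes a subject ineligible. In an eligible randomized subject, a topical that ended before Day 1 is therefore not trial rescue.

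**Will such records be in the database?** Probably. Protocol 9.6 asks for prior AD therapies to be documented whenever possible, and its definition of prior therapy covers those stopped in the 3 months before screening, or longer ago if relevant to eligibility. Protocol 7.1 requires a documented history of inadequate response to topical AD medication.

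**How would the fourth row arise?** Table 3 in Protocol 9.6.2 restricts TCS and TCI for 2 weeks before baseline in subjects without a stable regimen. The note under that table says such treatments should not be discontinued for reasons related to the study. Stopping for other reasons remains possible, so this is the secondary route. The third row is the main one.

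**Is the wider rule a declared change?** The visible text of SAP Section 14 records one for concomitant therapy in 14.1 ("Concomitant medications/therapies are defined as medications/ therapies which start or stop on or after the 1st injection of study drug") but none for background therapy.

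**The case against.** The best reply is that the team means the protocol's definition. SAP 3.3 restates it, and the 7.6 bullet is one line in a list of tables that may only say which records to tabulate. Silence in Section 14 fits the view that no change was intended. SAP 7.6 also lists background TCS dispensation or receipt, and Protocol Appendix 4 names background topical therapy among the items to collect remotely, so a subgroup flag need not come from dates at all.

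Much of this stands. SAP 7.6 is the only visible operational rule, not the only statement of what background therapy means. The subgroup consequence is conditional: 6.6 does not cite 7.6, and the efficacy analysis section and Section 20 cannot be seen and may hold a subgroup rule.

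It does not rescue the wording of 7.6. Automatic identification by code followed by a date condition is what will be programmed, and a listing of dispensed TCS is not a classification rule. Intent in 3.3 and a different filter in 7.6 are a reason to align them.

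A reader might go further and infer that nearly every subject would be flagged, leaving almost no one without background therapy, because eligibility requires past topical failure. The documents do not support that. The topical medication need not have been a TCS or TCI, documentation of prior AD therapy is asked for whenever possible, and no counts are given.

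**Conclusion.** The point holds as a minor inconsistency. Applied literally, SAP 7.6 counts as background therapy topicals that had stopped by screening, and non-stable regimens stopped before Day 1, contrary to Protocol 7.1 and 9.6.1.1 and to SAP 3.3. The direct consequence is an overstated Table 14.1.4.3.3, to the extent that such records exist. Misclassification in the SAP 6.6 subgroups follows only if they use the same flag.

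The size is unknown: the documents give neither the number of background users nor the number with earlier TCS or TCI. It should not be read as a threat to the main result. The primary analysis is stratified by baseline disease severity and run on the mITT population, and neither depends on background therapy. The subgroups are declared exploratory.

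**What to change.** Change the SAP only.

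1. In 7.6, define background therapy as a stable TCS regimen of low or medium potency, with or without TCI, in use at the screening visit and not classified as rescue. In date terms: started on or before screening, and either ongoing or stopped after the screening visit.
2. Dates alone do not prove stability. Resolve unclear cases at the blind data review, using the site's record of background therapy.
3. Decide subjects on stable TCI alone at the same review. Protocol 7.1 speaks of TCS with or without TCI, whereas 9.6.1.3 mentions TCI background therapy without requiring TCS, and Table 3 does not prohibit stable TCI.
4. Have SAP 6.6 refer to this definition, fixed before unblinding.

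The cost is a sentence or two in 7.6, a cross-reference in 6.6 and an agenda item at a meeting that Protocol Section 16 already provides for. The SAP already works with medication start and stop dates, so no new data collection is needed. Potency would have to be read from the recorded product.

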# 8. Vaccine Response Analysis

## 8.1. Primary Vaccine Response Endpoint and Analysis

# **8.1.1.** Primary Analysis of Primary Endpoint

The primary endpoint of this study is the proportion of subjects with a positive serum IgG response to tetanus toxoid at Week 16 (4 weeks post-vaccination), defined as:

- ≥ 4-fold increase in anti-tetanus IgG concentrations from baseline in subjects with pre-vaccination anti-tetanus IgG concentrations ≥ 0.1 IU/mL, OR
- ≥ 0.2 IU/mL anti-tetanus IgG concentrations in subjects with pre-vaccination anti-tetanus IgG concentrations < 0.1 IU/mL

Anti-tetanus IgG concentrations and the ratio from baseline will be summarized by treatment group and by visit using descriptive statistics.

The analysis for primary endpoint will be using the Cochran-Mantel-Haenszel (CMH) estimate of the risk difference and corresponding 2-sided 90% CI. It will be adjusted for the randomization stratum baseline using weighted average of stratum-specific proportion using CMH.

The example SAS code for CMH model is included in Section 20.1. The primary analysis will be conducted on the mITT population.

Subjects in receipt of systemic rescue medication will not be vaccinated. As the primary analysis will be conducted on the mITT, no imputation is required.

#### **8.1.2.** Sensitivity Analysis of Primary Endpoint

Three sensitivity analyses will be performed on ITT population and the same statistical testing as the primary analysis will be performed:

- Non-responder Imputation: any subjects without an evaluable vaccine response will be
  regarded as a Non-Responder. Non-evaluable vaccine response: defined as a response that
  cannot be classified as positive or negative due to missing assessment for the endpoint.
- **Observed Case**: No data will be imputed. All data as observed will be included in the analysis and the percentage will be calculated based on the number of observation available.
- COVID-19 Affected Case: Removal of subjects with COVID-19 (i.e. exclusion of subjects who
  had COVID-19).

# **8.1.3.** Subgroup Analysis of Primary Endpoint

The subgroup analyses as specified in section 6.6 will be performed for the primary endpoints on mITT population:

[figure not shown]
The results from the analysis will be presented as forest plot summarizing frequencies in each treatment group, risk difference and the corresponding 2-sided 90% CI on each subgroup.

# 8.2. Secondary Vaccine Response Endpoints and Analyses

The following secondary vaccine response endpoints are to be analysed:

- Proportion of subjects with a positive serum IgG response to tetanus toxoid at Week 16 (≥ 2-fold increase in anti-tetanus IgG concentration from baseline in subjects with pre-vaccination anti-tetanus IgG concentration ≥ 0.1 IU/mL OR ≥ 0.2 IU/mL anti-tetanus IgG concentrations in subjects with pre-vaccination anti-tetanus IgG concentrations < 0.1 IU/mL)

- Proportion of subjects with serum anti-tetanus IgG concentrations of ≥ 0.1 IU/mL at Week 16
- Proportion of subjects with serum anti-tetanus IgG concentrations of ≥ 1.0 IU/mL at Week 16
- Proportion of subjects with a positive serum bactericidal antibody response to meningococcal serogroup C polysaccharide at Week 16 (4 weeks post-vaccination) defined as ≥ 4-fold increase in SBA reciprocal titer from baseline
- Proportion of subjects with a positive serum bactericidal antibody response to meningococcal serogroup C polysaccharide at Week 16 defined as SBA reciprocal titer ≥ 8

[figure not shown]

[figure not shown]

**Statistical Analysis Plan**Sponsor: Galderma S.A./Galderma R&D, LLC; Protocol No.: RD.06.SPR.118380 V4.0, 06Jul2022

[figure not shown]
SAP Version: 5.0, 15Feb2024 Controlled Document ID: **3903A.01**, Effective Date 29-Oct-2018 Filing requirements: TMF

This document is confidential.

SAP Version: 5.0, 15Feb2024 Controlled Document ID: **3903A.01**, Effective Date 29-Oct-2018 Filing requirements: TMF

This document is confidential.

SAP Version: 5.0, 15Feb2024 Controlled Document ID: **3903A.01**, Effective Date 29-Oct-2018 Filing requirements: TMF

# 10. Safety Analysis

The population used for safety analyses will be the SAF.

#### 10.1. Extent of Exposure

The extent of exposure will be summarized by treatment group as follows:

- Treatment duration (in days): calculated as [(date of last treatment date of first treatment) + 1],
- the number of subjects exposed to study drug at visit Baseline, Week 4, Week 8 and Week 12,
- Cumulative dose received (mg): calculated as sum of all dose of study drug administered
- The number of subjects who received vaccines (Tdap and MCV4 and overall) at Week 12.
- The number of subjects missed at least one dose and the number of doses missed due to COVID-19, i.e. the reason for dose not administered reported in eCRF is related to COVID-19
- The subject with Vaccine injection missed due to COVID-19, i.e. the reason for dose not administered reported in eCRF is related to COVID-19

Extent of exposure information, study drug administration and vaccine administration will be listed, separately.

### 10.2. Treatment Compliance

Dose modification of the study drug (nemolizumab 30 mg or Placebo) will not be permitted during the clinical study.

Treatment compliance of study drug will be calculated as the ratio (expressed as percentage) between the total number of actual injections and the total number of expected injections.

The total number of actual injections will be counted based on collected study drug administration data. The total number of expected injections will be counted based on the following dosage schedule.

Table 2: Treatment Period Dosing By Treatment Group

Treatment Group	Dose/route	Week(s)	Schedule
Nemolizumab (CD14152)	30 mg × 2 SC injections	Baseline	Baseline
	30 mg × 1 SC injections	4, 8, 12	Q4W
Placebo	Placebo× 2 SC injections	Baseline	Baseline
	Placebo× 1 SC injections	4, 8, 12	Q4W

Abbreviation(s): Q4W=every 4 weeks; SC=subcutaneous.

The compliance data will be listed and summarized by treatment group.

